5.2 Description of Study Design

The design of this clinical study is a prospective, open-label, multicenter, non-randomized clinical investigation, where the effects of LASIK in correcting myopia and myopic astigmatism are evaluated by comparing post-operative refraction and visual acuity to standard guidelines. The study treatment range (indication for use) includes up to MRSE -11.50 D.

The study will involve an evaluation of approximately 334 treated eyes at up to 12 investigational sites, with a final sample size of at least 300 study eyes evaluable at the final visit. Every effort will be made to enroll approximately the same number of eyes at each investigational site. The additional 34 study eyes will allow for losses up to 10% due to early subject discontinuation. Both eyes of a subject may be enrolled. Subjects will be permitted to have both eyes enrolled so long as both eyes meet all inclusion/exclusion

requirements. Analyses will include all enrolled eyes treated with the TENEO 317 laser. Enrollment will be limited to subject eyes with sphere of -1.0 D up to -10.00 D, cylinder between 0.0 D and -3.0 D; with a manifest refraction spherical equivalent (MRSE) between -1.0 D and -11.50 D.

Enrolled subjects can possibly attend up to 8 study visits. It is planned to enroll and treat approximately 334 subject eyes, with an expectation that approximately 300 study eyes will complete post-surgical follow-up for 9 months. All subjects, regardless of the time of individually achieving refractive stability, will be followed up until the last study visit (Visit 8) which is Month 9 post-operatively.

For completed subjects, it is planned to have ≥ 20 eyes per each diopter (see Dioptric Bins, **Table 1**) of spherical correction to be studied and ≥ 30 eyes per dioptric bin of cylinder correction to be studied. Of the eyes in the -0.25 to -1.0 D astigmatism range, at least 30 eyes are planned to be in each of the -0.25 to -0.5 D and the -0.5 to -1.0 D astigmatism ranges (see **Table 1**, Bin Table).

A 180-Day PMA supplement application will be submitted to the FDA when the enrolled study cohort has completed approximately 9 months of safety and effectiveness assessments post-surgery (cf. **Appendix A**).

		Cylinder (in minus notation				
	0 Cylinder (Sphere Only)	-0.25 to -0.5 D	-0.51 to -1 D	-1.01 to -2 D	-2.01 to -3 D	Total
Sphere (in minus notation)	n	n	n	n	n	n
-1 to -2 D	> 0	> 0	> 0	> 0	> 0	≥ 20
-2.01 to -3 D	> 0	> 0	> 0	> 0	> 0	≥ 20
-3.01 to -4 D	> 0	> 0	> 0	> 0	> 0	≥ 20
-4.01 to -5 D	> 0	> 0	> 0	> 0	> 0	≥ 20
-5.01 to -6 D	> 0	> 0	> 0	> 0	> 0	≥ 20
-6.01 to -7 D	> 0	> 0	> 0	> 0	> 0	≥ 20
-7.01 to -8 D	> 0	> 0	> 0	> 0	> 0	≥ 20
-8.01 to -9 D	> 0	> 0	> 0	> 0	> 0	≥ 20
-9.01 to -10 D	> 0	> 0	> 0	> 0	> 0	≥ 20
Total	>3 0	\geq 30	≥ 30	≥ 3 0	≥ 3 0	≥ 300

 Table 1. LASIK Preoperative "Dioptric Bin" Enrollment Plan

TENEO 317 1.28 US

B+L Study # 884 Protocol Ver 8.0 Bausch Health Research and Development

5.2.1 Fellow Eye Treatments

Because unilateral enrollment would result in subjects with a significant degree of anisometropia, and the safety and effectiveness of the TENEO 317 Model 2 excimer laser (ver. 1.28 US SW) specific to the treatment of myopia or myopic astigmatism are supported by retrospective data, bilateral LASIK treatments will be permitted in this study. Both eyes may be enrolled for efficacy and safety assessments if the subject is fully informed that the surgical risks apply equally to each eye. If an intraoperative complication or adverse event occurs in the first eye, treatment must be abandoned in the second eye. Each eye treated according to this protocol for an enrolled subject will be reported on separately and included in the data analysis.

5.2.2 Enhancement and Retreatment Procedures

If the treated eye remains under-corrected and/or corneal haze or vision regression decreases to UDVA of 20/30 or worse, then an enhancement or retreatment may be performed. No enhancement or retreatment may be performed before a subject exits the study.

5.2.3 Description for Use of Pre-vs-Post Subjective Patient Questionnaire (PROWL)³⁴⁻³⁷

The pre-operative and post-operative PROWL (Patient Reported Outcomes with LASIK) questionnaires were developed and validated to sample patient impressions of LASIK surgery adequacy for improved vision and activities such as night driving, sports, etc. dependent on good patient vision. Select PROWL questions and domains will be analyzed for this study, not the PROWL-PRQ and PROWL-POQ questionnaires in their entirety. However, the entire PROWL questionnaires are included in this study since they were validated as such.^{36,37} PROWL questions and domains relating to subject subjective preoperative and postoperative impressions of their LASIK surgery^{36,37} (including clusters of questions or domains for vision clarity, far vision, near vision, patient satisfaction with vision and with surgery, and quality of life) and patient-perceived safety assessments (i.e., driving, dry eye [OSDI domains 1 and 3],^{38,39} and the frequency, severity, and bothersomeness of visual symptoms) will be analyzed as described in Section 8.5 and Section 9.6.3.3.1 and by the methods and respective scoring methodologies for each of the above domains as detailed in the study Statistical Analysis Plan. The PROWL questionnaires^{34, 35} should be completed by the study subject in a secluded area, free of directions from clinical staff.

5.3 Selection of Study Population

- 5.3.1 Eligibility^{40, 41}
- 5.3.1.1 Inclusion Criteria:
- 1. Are 22 years of age or older.
- 2. Have read, understood, and signed an informed consent form (ICF).
- 3. Have demonstrated stable refraction (i.e., a change of ≤ 0.5 D in sphere and cylinder) for a minimum of 12 months prior to surgery, verified by consecutive refractions and/or medical records or prescription history.
- 4. Have myopic refractive error with or without astigmatism; sphere between -1.0 D and -10.00 D, cylinder between 0.0 D and -3.0 D; with a manifest refraction spherical equivalent (MRSE) between -1.0 D and -11.50 D.
- 5. Have uncorrected distance visual acuity (UDVA) of 20/40 or worse.
- 6. Have manifest best spectacle corrected distance visual acuity (BSCVA) of 20/25 (logMAR 0.1) or better in an operative eye.
- 7. Have less than or equal to 0.50 D spherical equivalent (SE) difference between cycloplegic and manifest refractions at Visit 1 (Pre-operative).
- 8. Have normal corneal topography as determined by the Investigator.
- 9. Have discontinued use of contact lenses for at least 2 weeks (for hard or toric lenses) or 3 days (for soft contact lenses) prior to the pre-operative examination, and through the day of surgery.
- 10. All contact lens wearers must demonstrate a stable refraction (within \pm 0.5 D), as determined by MRSE, on two consecutive examinations at least 1 week apart, in an eye to be treated and the axis of cylinder should not differ by more than 15 degrees.
- 11. Have the ability to lie flat without difficulty.
- 12. Are willing and able to comply with the schedule for all post-surgery follow-up visits.

5.3.1.2 Exclusion Criteria:

- 1. Subjects for whom the combination of their baseline corneal thickness and the planned operative parameters for the LASIK procedure would result in treatment depth less than 250 microns from corneal endothelium.
- 2. Eyes for which the baseline manifest subjective refraction exhibits a difference greater than 0.50 D in sphere power, or a difference greater than 0.50 D in cylinder power, or a difference in cylinder axis of more than 15 degrees compared to the baseline cycloplegic subjective refraction. For manifest cylinder of less than 0.50 D, the difference in cylinder axis will not be taken into consideration.

- 3. Subjects for whom the pre-operative assessment of the cornea indicates that one or both eyes are not suitable candidates for treatment based upon the Investigator's medical judgment.
- 4. Have evidence of retinal vascular disease.
- 5. Have a history of or have active corneal disease or infection (e.g., recurrent corneal erosion syndrome, herpes simplex or herpes zoster keratitis, etc.) in an eye.
- 6. Have a known sensitivity to any study medication.
- 7. Have central corneal scars affecting visual acuity or unstable keratometry with irregular mires in an eye considered for eligibility.
- 8. Have keratoconus, subclinical or forme fruste keratoconus, corneal dystrophy or other corneal irregularity (e.g., irregular astigmatism).
- 9. Have visually significant or progressive cataract in an eye considered for eligibility.
- 10. Had previous intraocular or corneal surgery in an eye considered for eligibility that might confound the outcome of the study or increase the risk to the subject.
- 11. Use chronic medications by any administration route that may increase risk to the subject or may confound the outcome of the study, including those known to affect wound healing (e.g., corticosteroids, antimetabolites, etc.).
- 12. Are known to have acute or chronic disease or illness (e.g., dry eye, cataract, glaucoma, immuno-compromised, rheumatoid arthritis, clinically significant atopic disease, acne rosacea, etc.) that would increase operative risk or may confound the results of the study.
- 13. Are taking medications contraindicated for LASIK such as isotretinoin (Accutane) or amiodarone hydrochloride (Cordarone).
- 14. Are known to be pregnant, lactating, or who plan to become pregnant during the course of the study.
- 15. Have known sensitivity to medications used for standard LASIK.
- 16. Have the presence of systemic disease likely to affect wound healing, e.g., autoimmune disease, systemic connective tissue disease, diabetes, or severe atopic disease.
- 17. Are participating in any other ophthalmic clinical trial within 30 days of screening or during this clinical trial.
- 18. Have an ocular muscle disorder including a strabismus or nystagmus, or other disorder affecting fixation.
- 19. Have a history of or evidence of glaucoma or are a glaucoma suspect.
- 20. Have eyes with mesopic pupil size > 7.0 mm.
- 21. Have a Schirmer's pre-operative test without anesthesia < 4 mm/5 minutes

Subjects failing to meet eligibility criteria prior to scheduling of surgery are considered screen failures.

5.3.2 Subject Enrollment

The subject must satisfy all eligibility criteria prior to enrollment. The subject is considered enrolled in the study at the time they sign the informed consent form (which includes consent to have photo and video recordings of the eye surgery made), with the study eye selected by the Investigator at the first study visit (Pre-operative). It is understood the number of subject eyes enrolled at the first study visit may be slightly more than the target number of 334 treated eyes.

5.3.3 Subject Completion

The subject has completed the entire study when the LASIK refractive surgery has been completed and the Sponsor receives completed eCRF documentation for all required visits and a study exit eCRF. Subjects who require further follow-up for an AE will be followed until the AE has resolved or remitted, **regardless of whether they have completed all study visits**.

A Study Exit eCRF must be completed for all subjects who complete or are early discontinued from the clinical investigation.

5.3.4 Subject Discontinuation

A subject MAY discontinue prior to the final study visit due to an AE occurring during the study which requires further medical intervention. A subject MUST be discontinued prior to the final study visit if they voluntarily withdraw for any reason, it is the Investigator's decision that it is not in the best medical interest of the subject to continue participation in the study, or in the event of death of the subject.

Prior to discontinuing a subject who voluntarily withdraws, every effort should be made to contact the subject, schedule a final study visit, and obtain as much follow-up data as possible. Regardless of the patient voluntary withdrawal, adverse events should continue to be followed by the investigator until they have resolved or remitted. Subject withdrawals will be documented clearly on the source document and applicable eCRF.

Discontinued subjects who withdraw consent should be followed outside of the study protocol according to the Investigator's normal post-operative standard of care.

A Study Exit eCRF must be completed for all subjects who discontinue from the clinical investigation. The reasons for subject withdrawal and discontinuation of any subject will be documented clearly on the applicable eCRF and recorded.

Subjects who discontinue the study prior to the surgical procedure will be considered screen failures and will not be recorded on the eCRF. Subjects who are discontinued during/after study LASIK surgery will not be replaced.

B+L Study # 884 Protocol Ver 8.0

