5.3.5 Lost to Follow-up

Subjects who do not return for the final visit, as defined by the visit window, and cannot be contacted, may be considered lost to follow-up. Subjects who do not return for the final visit will have at least 2 documented attempts made to contact the subject by telephone or email. If all other attempts fail, a certified, return receipt requested letter will be sent to the last known address.

All follow-up attempts will be documented and documentation will be kept with the subject's source documents, and the applicable eCRFs will be completed. Documentation of the contact attempts and, if appropriate, a copy of the certified letter will be maintained in the subject's study file. It is expected that lost to follow-up subjects will comprise < 10% of all study eyes.

The exit date for subjects who are lost to follow-up will be the date of the last study visit (scheduled or unscheduled) attended by the subject.

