7.1.5 Missed Visits

If a subject misses any scheduled follow-up visit and cannot be seen prior to the start of the visit interval for the next scheduled follow-up visit, the visit is considered missed. A visit would be considered a Missed Visit if neither a Telephone Contact nor an OOW Visit to complete the assessments was performed.

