6.4.1 Effectiveness Variables

Data for the following primary effectiveness endpoints will be evaluated statistically at the achievement time for refractive stability. Since the time of achievement for refractive stability cannot be predicted *a priori*, the effectiveness endpoints will be evaluated at 1-month, at 3 months, and at 6 months. In the absence of refractive stability occurring by 6 months post-surgery, the primary effectiveness endpoints will also be evaluated at 9 months post-surgery.

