6.5.8 Safety Analyses

The following safety summaries will be provided with descriptive statistics by visit for all treated eyes, eyes treated for spherical myopia, and eyes treated for astigmatic myopia unless otherwise specified.

- Eyes with BSCVA worse than 20/40 among eyes that had a BSCVA of 20/20 or better before surgery at each postoperative study visit, stratified by preoperative MRSE in 1.00-D unit ranges from -1.00 D to -12.00 D; by severity of preoperative myopia with > -7 D and <= -7 D; and by preoperative cylinder for ranges of 0, -0.25 to -0.50 D, -0.51 to -1.00 D, -1.01 D to -2.00 D, and -2.01 D to -3.00 D
- Loss of BSCVA of 1, 2, ≥ 2, and > 2 lines compared to preoperative BSCVA, with 95% CIs around the proportions
- Percentage of eyes that have an increase of manifest refractive astigmatism > 2.00
 D compared to the preoperative refraction (since all cylinder values will be converted to minus notation first, this is equivalent to change from baseline in cylinder <= -2 D), stratified by preoperative MRSE, and severity of preoperative myopia. A 95% CI around the percentage of all eyes that have an increase of > 2.00
 D will be displayed.
- Incidence of AEs by event type
- Incidence of complications
- Endothelial cell density changes
- Contrast sensitivity changes, mesopic conditions
- Subject symptoms and results for prespecified question domains (from Patient Reported Outcome with LASIK - Preoperative Questionnaire [PROWL-PRQ] [3] and Patient Reported Outcome with LASIK - Postoperative Questionnaire [PROWL-POQ] [4])

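### An AE may end scheduled assessments after one-time surgery, and minimum contact attempts cover only the final visit, so later by-visit safety rows can look too favourable

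*Protocol*

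**What the plan says.** **Leaving for an AE.** Protocol 5.3.4: "A subject MAY discontinue prior to the final study visit due to an AE occurring during the study which requires further medical intervention". Protocol 5.2 and the closing paragraph of 7.1.3.5 say that all subjects are followed to Visit 8 at Month 9, whenever they individually reach stability. Protocol 7.1 makes an exception for early discontinuation.

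**What continues after leaving.** Protocol 5.3.3: "Subjects who require further follow-up for an AE will be followed until the AE has resolved or remitted", whether or not all visits are completed. For a subject who withdraws voluntarily, 5.3.4 adds that "every effort should be made to contact the subject, schedule a final study visit, and obtain as much follow-up data as possible". That duty is not worded for an exit because of an AE.

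**Contact attempts.** Protocol 5.3.5: "Subjects who do not return for the final visit will have at least 2 documented attempts made to contact", by telephone or email, and then a certified letter. For an interim visit, 7.1.5 says only that if the subject "cannot be seen prior to the start of the visit interval for the next scheduled follow-up visit, the visit is considered missed". Disruption by COVID-19 has its own telephone and recall procedure (7.1.3.5, 7.4.1.2).

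**When the primary endpoints are read.** They are read at the cohort's stability visit. SAP 6.4.1 says its time cannot be predicted and provides for Months 1, 3 and 6, then: "In the absence of refractive stability occurring by 6 months post-surgery, the primary effectiveness endpoints will also be evaluated at 9 months post-surgery".

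**Safety tables.** SAP 6.5.8 plans by-visit summaries that include "Loss of BSCVA of 1, 2, ≥ 2, and > 2 lines compared to preoperative BSCVA", BSCVA worse than 20/40 among eyes that were 20/20 or better before surgery, and astigmatism increase above 2.00 D. It describes no imputation or worst-case version of them.

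**The concern.** After a one-time operation there is no study treatment to stop. An exit because of an AE therefore ends only the measurements, and it does so in subjects whose outcomes matter most for safety. Exit is by subject, so an untroubled fellow eye goes too. From then on the eye is in neither the numerator nor the denominator of the by-visit acuity and astigmatism rows. If the eyes that leave did worse than those that stay, the later rows are biased in the device's favour.

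The second gap concerns retention for the primary endpoints. If stability is declared at Month 3 or 6, a refraction missed at that visit cannot be recovered by calls triggered by non-return at Month 9. Outside COVID-19 disruption, no minimum effort is set for the interim visit itself.

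**Working it through.** **1. The plan's own figures.** Treated eyes: 300/(1 − 0.10) = 333.3, rounded up to 334, as stated. Power at n = 300, one-sided 0.025, is Φ{[√n(π₁ − π₀) − 1.96√(π₀(1 − π₀))]/√(π₁(1 − π₁))}. For ±1.00 D (0.90 against 0.99) this is Φ{[1.559 − 0.588]/0.0995} = Φ(9.8). For ±0.50 D (0.80 against 0.945) it is Φ(7.6), and for UDVA (0.88 against 0.99) Φ(12.7). All exceed 99.99%, as stated.

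**2. Where an eye that leaves for an AE still counts.**
- AE table: all treated eyes, with a Total column; AEs leading to discontinuation are listed separately (SAP 6.5.8.3). Loss of more than 2 lines, BSCVA worse than 20/40 and astigmatism increase above 2.0 D are themselves listed AEs, so an event already recorded is kept.
- Primary endpoints: all treated eyes through multiple imputation (SAP 6.5.6.2), with observed-case, best-case and worst-case analyses (SAP 6.5.6.3). The imputation uses only the same variable's values from Week 1 to Month 9, with no term for the AE or the reason for exit.
- By-visit BSCVA and astigmatism tables (SAP 6.5.8): not after exit.
- Events that need later examinations, such as a BSCVA decrease at 3 months or later or haze beyond 6 months (Protocol 8.1): nothing requires those scheduled examinations after exit, in either eye.

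**3. Size in the by-visit tables (assumed counts).** Suppose 300 eyes would be seen at Month 9 and 3 have lost more than 2 lines. Exact limits are my choice; the SAP names no method for this table.
- All stay: 3/300 = 1.0% (95% CI 0.21% to 2.89%).
- All three subjects are bilateral and leave: 300 − 6 = 294, so 0/294 = 0%, upper limit 1 − 0.025^(1/294) = 1.25%.

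A range, counting affected eyes only, with 7 events in 334 (2.1%):

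| Affected eyes leaving | Row shows |
|---|---|
| 2 | 5/332 = 1.5% |
| 4 | 3/330 = 0.9% |
| 7 | 0/327 = 0% |

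**4. Accountability.** SAP 6.5.1 divides eyes available by enrolled minus discontinued minus active eyes. With 6 of 334 eyes discontinued, none active and no other loss, it gives 328/(334 − 6) = 100%, against 328/334 = 98.2% of all enrolled eyes. The number discontinued is displayed, but the reasons are only listed.

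**5. Size for the primary tests.** The SAP rule on 334 eyes needs 310 successes for ±1.00 D: 310/334 = 92.8%, lower limit 90.04%. If k eyes leave for an AE and all are failures, power at a 99% rate in the rest is P{Bin(334 − k, 0.99) ≥ 310}. This exceeds 99.99% for k = 3, 7 and 10, and is 98.5% for k = 17.

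The full planned loss is more serious. Take 34 missing eyes, all failures, with 300 observed at the assumed rates (all targeted for emmetropia):

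| Endpoint | Result | Lower limit | Null | Missing failures tolerated |
|---|---|---|---|---|
| ±0.50 D | 284/334 = 85.0% | 81.2% | 80% | all 34 |
| ±1.00 D | 297/334 = 88.9% | 85.6% | 90% | 21 |
| UDVA | 297/334 = 88.9% | 85.6% | 88% | 26 |

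Two of the three endpoints would fail. This is an extreme bound on all missing data, not an estimate for AE exits.

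**The case against.** The strongest reply is that little is lost. Recorded events remain in the AE table, AEs are followed until resolved or remitted, and the primary analysis keeps every treated eye. That stands, and it limits the point to later by-visit rows and to findings that need later examinations.

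A second reply is that retention need not restore the illustrated 3/300: an eye that recovers after treatment would show no loss at Month 9 either. That is fair. The row would then at least report the eye's actual outcome, provided values after an intervention are flagged.

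A third is that Protocol 5.2.2 and SAP 6.1.2 bar enhancement or retreatment before study exit, so exit is also the route to a retreatment. This is right, and it means that retention cannot simply be imposed; the sections have to be reconciled.

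On contact, a reader might infer that it is required only at Month 9. The documents do not support that: voluntary withdrawal at any time and COVID-19 disruption have their own provisions. What is missing is a documented minimum for a missed interim visit outside COVID-19. The Study Reference Manual (Protocol 5.4) covers discontinuation and may say more; it is not among the documents.

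**Conclusion.** The point holds in limited form. Protocol 5.3.4 allows scheduled measurements to stop because of an AE after a one-time procedure, and this sits uneasily with the statements that all subjects are followed to Visit 8. The by-visit BSCVA and astigmatism tables have no protection against the resulting loss, and the accountability percentage does not show it. The minimum contact attempts are tied to a visit that may not be the primary time point.

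A reader might go further and infer that these outcomes vanish from the safety reporting or the primary analysis, or that the SAP expects stability at Month 3 or 6. None of this is supported: the AE table, multiple imputation and worst-case analysis keep the eyes, and the SAP calls the time unpredictable.

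The size is illustrative. The documents give no AE-exit rate, the exit is optional, and the 0/294 case assumes that every affected subject is bilateral and leaves. AE exits of up to 10 eyes, even if all were failures, would leave the primary tests with more than 99.99% power under the plan's assumed rates.

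**What to change.** 1. **Protocol 5.3.4.** State that an AE alone does not end scheduled data collection. The subject stays on the existing visit schedule, with each treated eye assessed, unless consent is withdrawn, the subject dies or is lost to follow-up, or the investigator documents that continuing is against the subject's interest. Care of the AE remains with the investigator. Reconcile this wording with Protocol 5.2, 7.1 and 7.1.3.5 (follow-up to Visit 8) and with Protocol 5.2.2 and SAP 6.1.2 (no enhancement or retreatment before study exit). No retreatment rule is proposed here. Flag values recorded after an intervention, by eye and date.
2. **Protocol 5.3.5.** Require the same two documented contact attempts for a missed Month 1, 3 or 6 visit, made while that visit can still be completed.

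**Cost.** The visits are already scheduled. The change adds some site calls and a data flag. It needs a protocol amendment with IRB approval before implementation (Protocol 10.7), and a revised consent form if the amendment requires one. It helps only subjects still in follow-up; Protocol 7.4.1.1 shows that some had been treated by March 2020.
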